4.2.2 Dose Modification

Adverse events (both non-serious and serious) associated with pembrolizumab exposure may represent an immunologic etiology. These adverse events may occur shortly after the first dose or several months after the last dose of treatment. Pembrolizumab must be withheld for drug-related toxicities and severe or life-threatening AEs as per Table 2 below. See Section 4.4 and Events of Clinical Interest Guidance Document for supportive care guidelines (Appendix C), including use of corticosteroids.

Table 2 Dose Modification Guidelines for Drug-Related Adverse Events

Toxicity	Hold Treatment For Grade	Timing for Restarting Treatment	Treatment Discontinuation
Diarrhea/Colitis	2-3	Toxicity resolves to Grade 0-1.	Toxicity does not resolve within 12 weeks of last dose or inability to reduce corticosteroid to 10 mg or less of prednisone or equivalent per day within 12 weeks.
	4	Permanently discontinue	Permanently discontinue
AST, ALT, or Increased Bilirubin	2	Toxicity resolves to Grade 0-1	Toxicity does not resolve within 12 weeks of last dose.
	3-4	Permanently discontinue (see exception below) ¹	Permanently discontinue
Type 1 diabetes mellitus (if new onset) or Hyperglycemia	T1DM or 3-4	Hold pembrolizumab for new onset Type 1 diabetes mellitus or Grade 3-4 hyperglycemia associated with evidence of beta cell failure.	Resume pembrolizumab when patients are clinically and metabolically stable.
Hypophysitis	2-4	Toxicity resolves to Grade 0-1. Therapy with pembrolizumab can be continued while endocrine replacement therapy is instituted	Toxicity does not resolve within 12 weeks of last dose or inability to reduce corticosteroid to 10 mg or less of prednisone or equivalent per day within 12 weeks.
Hyperthyroidism	3	Toxicity resolves to Grade 0-1	Toxicity does not resolve within 12 weeks of last dose or inability to reduce corticosteroid to 10 mg or less of prednisone or equivalent per day within 12 weeks.
	4	Permanently discontinue	Permanently discontinue
Hypothyroidism		Therapy with pembrolizumab can be continued while thyroid replacement therapy is instituted	Therapy with pembrolizumab can be continued while thyroid replacement therapy is instituted.

Toxicity	Hold Treatment For Grade	Timing for Restarting Treatment	Treatment Discontinuation
Infusion Reaction	3-4	Permanently discontinue	Permanently discontinue
Pneumonitis	2	Toxicity resolves to Grade 0-1	Toxicity does not resolve within 12 weeks of last dose or inability to reduce corticosteroid to 10 mg or less of prednisone or equivalent per day within 12 weeks.
	3-4	Permanently discontinue	Permanently discontinue
Renal Failure or Nephritis	2	Toxicity resolves to Grade 0-1	Toxicity does not resolve within 12 weeks of last dose or inability to reduce corticosteroid to 10 mg or less of prednisone or equivalent per day within 12 weeks.
	3-4	Permanently discontinue	Permanently discontinue
All Other Drug-Related Toxicity ²	3 or Severe	Toxicity resolves to Grade 0-1	Toxicity does not resolve within 12 weeks of last dose or inability to reduce corticosteroid to 10 mg or less of prednisone or equivalent per day within 12 weeks.
	4	Permanently discontinue	Permanently discontinue

Note: Permanently discontinue for any severe or Grade 3 drug-related AE that recurs or any life-threatening event.

¹ For patients with liver metastasis who begin treatment with Grade 2 AST or ALT, if AST or ALT increases by greater than or equal to 50% relative to baseline and lasts for at least 1 week then patients should be discontinued.

² Patients with intolerable or persistent Grade 2 drug-related AE may hold study medication at physician discretion. Permanently discontinue study drug for persistent Grade 2 adverse reactions for which treatment with study drug has been held, that do not recover to Grade 0-1 within 12 weeks of the last dose.

Dosing interruptions are permitted in the case of medical / surgical events or logistical reasons not related to study therapy (e.g., elective surgery, unrelated medical events, patient vacation, and/or holidays). Subjects should be placed back on study therapy within 3 weeks of the scheduled interruption, unless otherwise discussed with the Sponsor. The reason for interruption should be documented in the patient's study record.

In case toxicity does not resolve to Grade 0-1 or baseline within 12 weeks after last infusion, trial treatment will be discontinued. Subjects with a laboratory adverse event still at Grade 2 after 12 weeks may continue treatment in the trial only if asymptomatic and controlled.

Subjects who experience a recurrence of the same severe or life-threatening event at the same grade or greater with re-challenge of MK-3475 will be discontinued from trial treatment.

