4.4 Rescue Medications & Supportive Care

Subjects should receive appropriate supportive care measures as deemed necessary by the treating investigator. Suggested supportive care measures for the management of adverse events with potential immunologic etiology are outlined below and in greater detail in the ECI guidance document (Appendix C in PDOL). Where appropriate, these guidelines include the use of oral or intravenous treatment with corticosteroids as well as additional anti-inflammatory agents if symptoms do not improve with administration of corticosteroids. Note that several courses of steroid tapering may be necessary as symptoms may worsen when the steroid dose is decreased. For each disorder, attempts should be made to rule out other causes such as metastatic disease or bacterial or viral infection, which might require additional supportive care. The treatment guidelines are intended to be applied when the investigator determines the events to be related to pembrolizumab.

Note: if after the evaluation the event is determined not to be related, the investigator is instructed to follow the ECI reporting guidance but does not need to follow the treatment guidance (as outlined in the ECI guidance document). Refer to Section 4.2.2 for dose modification.

It may be necessary to perform conditional procedures such as bronchoscopy, endoscopy, or skin photography as part of evaluation of the event. Suggested conditional procedures, as appropriate, can be found in the ECI guidance document (Appendix C in PDOL).

- **Pneumonitis:**

- For **Grade 2 events**, treat with systemic corticosteroids. When symptoms improve to Grade 1 or less, steroid taper should be started and continued over no less than 4 weeks.
- For **Grade 3-4 events**, immediately treat with intravenous steroids. Administer additional anti-inflammatory measures, as needed.
- Add prophylactic antibiotics for opportunistic infections in the case of prolonged steroid administration.

- **Diarrhea/Colitis:**
Subjects should be carefully monitored for signs and symptoms of enterocolitis (such as diarrhea, abdominal pain, blood or mucus in stool, with or without fever) and of bowel perforation (such as peritoneal signs and ileus).

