 - All subjects who experience diarrhea/colitis should be advised to drink liberal quantities of clear fluids. If sufficient oral fluid intake is not feasible, fluid and electrolytes should be substituted via IV infusion. For Grade 2 or higher diarrhea, consider GI consultation and endoscopy to confirm or rule out colitis.
 - For **Grade 2 diarrhea/colitis** that persists greater than 3 days, administer oral corticosteroids.
 - For **Grade 3 or 4 diarrhea/colitis** that persists > 1 week, treat with intravenous steroids followed by high dose oral steroids.
 - When symptoms improve to Grade 1 or less, steroid taper should be started and continued over no less than 4 weeks.

- **Type 1 diabetes mellitus (if new onset, including diabetic ketoacidosis [DKA]) or ≥ Grade 3 Hyperglycemia, if associated with ketosis (ketonuria) or metabolic acidosis (DKA)**
 - For **T1DM or Grade 3-4 Hyperglycemia**
 - Insulin replacement therapy is recommended for Type I diabetes mellitus and for Grade 3-4 hyperglycemia associated with metabolic acidosis or ketonuria.
 - Evaluate patients with serum glucose and a metabolic panel, urine ketones, glycosylated hemoglobin, and C-peptide.

- **Hypophysitis:**
 - For **Grade 2 events**, treat with corticosteroids. When symptoms improve to Grade 1 or less, steroid taper should be started and continued over no less than 4 weeks. Replacement of appropriate hormones may be required as the steroid dose is tapered.
 - For **Grade 3-4 events**, treat with an initial dose of IV corticosteroids followed by oral corticosteroids. When symptoms improve to Grade 1 or less, steroid taper should be started and continued over no less than 4 weeks. Replacement of appropriate hormones may be required as the steroid dose is tapered.

- **Hyperthyroidism or Hypothyroidism:**

Thyroid disorders can occur at any time during treatment. Monitor patients for changes in thyroid function (at the start of treatment, periodically during treatment, and as indicated based on clinical evaluation) and for clinical signs and symptoms of thyroid disorders.

- **Grade 2** hyperthyroidism events (and **Grade 3-4** hypothyroidism):

- In hyperthyroidism, non-selective beta-blockers (e.g. propranolol) are suggested as initial therapy.
 - In hypothyroidism, thyroid hormone replacement therapy, with levothyroxine or liothyroinine, is indicated per standard of care.

- **Grade 3-4** hyperthyroidism

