6.3.2 Serious Adverse Event Reporting (SAE)

6.3.2.1 Internal SAE reporting to IND Office

An adverse event or suspected adverse reaction is considered “serious” if, in the view of either the investigator or the sponsor, it results in any of the following outcomes:

- Death
- A life-threatening adverse drug experience – any adverse experience that places the patient, in the view of the initial reporter, at immediate risk of death from the adverse experience as it occurred. It does not include an adverse experience that, had it occurred in a more severe form, might have caused death.
- Inpatient hospitalization or prolongation of existing hospitalization
- A persistent or significant incapacity or substantial disruption of the ability to conduct normal life functions.
- A congenital anomaly/birth defect.

Important medical events that may not result in death, be life-threatening, or require hospitalization may be considered a serious adverse drug experience when, based upon appropriate medical judgment, they may jeopardize the patient or subject and may require medical or surgical intervention to prevent one of the outcomes listed in this definition. Examples of such medical events include allergic bronchospasm requiring intensive treatment in an emergency room or at home, blood dyscrasias or convulsions that do not result in inpatient hospitalization, or the development of drug dependency or drug abuse (21 CFR 312.32).

- **Important medical events as defined above, may also be considered serious adverse events. Any important medical event can and should be reported as an SAE if deemed appropriate by the Principal Investigator or the IND/IND Sponsor, IND Office.**
- All events occurring during the conduct of a protocol and meeting the definition of a SAE must be reported to the IRB in accordance with the timeframes and procedures outlined in “University of Texas M. D. Anderson Cancer Center Institutional Review Board Policy for Investigators on Reporting Unanticipated Adverse Events for Drugs and Devices”. Unless stated otherwise in the protocol, all SAEs, expected or unexpected, must be reported to the IND Office, regardless of attribution (within 5 working days of knowledge of the event).
- **All life-threatening or fatal events**, that are unexpected, and related to the study drug, must have a written report submitted within **24 hours** (next working day) of knowledge of the event to the Safety Project Manager in the IND Office.

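### Table 2's note permanently stops MK-3475 after any life-threatening event, but the diabetes/hyperglycemia and hypophysitis rows allow restart, and no precedence is stated

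*Combined protocol and SAP*

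**What the plan says.** Table 2 in Section 4.2.2 gives hold, restart and stop rules by toxicity and grade. A note beneath it applies to the whole table: "Permanently discontinue for any severe or Grade 3 drug-related AE that recurs or any life-threatening event".

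Three endocrine rows contain no permanent stop tied to Grade 4 or to a life-threatening event:

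- **Type 1 diabetes/hyperglycemia** (hold for T1DM or Grade 3-4): "Hold pembrolizumab for new onset Type 1 diabetes mellitus or Grade 3-4 hyperglycemia associated with evidence of beta cell failure", then "Resume pembrolizumab when patients are clinically and metabolically stable". No criterion for stopping is given.
- **Hypophysitis** (hold for Grade 2-4): "Toxicity resolves to Grade 0-1. Therapy with pembrolizumab can be continued while endocrine replacement therapy is instituted". The row stops treatment only if the toxicity has not resolved, or steroids cannot be tapered, within 12 weeks.
- **Hypothyroidism** (no grade given): "Therapy with pembrolizumab can be continued while thyroid replacement therapy is instituted".

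Section 4.2.2 does not define life-threatening. Section 6.3.2.1, on SAE reporting, defines it as placing the patient "at immediate risk of death from the adverse experience as it occurred". Section 4.4 expects serious endocrine events: one of its headings opens "Type 1 diabetes mellitus (if new onset, including diabetic ketoacidosis [DKA", and it also covers Grade 3-4 hypophysitis. On dosing it sends the reader back: "Refer to Section 4.2.2 for dose modification".

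**The concern.** Take a patient who develops ketoacidosis that puts her at immediate risk of death, and who is later stable on insulin. Under the note she is never dosed again. Under the row she resumes. The investigator cannot obey both.

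If the row is followed, a patient is re-exposed after a life-threatening reaction, against a written stop rule. If the note is followed, a patient whose cancer is controlled loses what remains of up to 24 months of treatment that the row would allow. With no stated order between the two, similar patients could be handled differently.

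**Working it through.** The plan states no figure on this point, so the check compares texts.

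**Step 1: what each row does at Grade 4.** Table 2 has ten toxicity rows.

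- Seven stop permanently at Grade 4 and agree with the note: diarrhea/colitis, AST/ALT/bilirubin (with a footnoted exception), hyperthyroidism, infusion reaction, pneumonitis, renal failure/nephritis, and all other drug-related toxicity.
- 10 − 7 = 3 do not: T1DM/hyperglycemia, hypophysitis and hypothyroidism.

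**Step 2: how strong the conflict is in those three.**

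- T1DM/hyperglycemia names Grade 4 and gives an instruction to resume. The conflict is direct.
- Hypophysitis names Grade 4 and makes recovery to Grade 0-1 the condition for restart. The conflict is explicit, although its sentence on hormone replacement is permissive.
- Hypothyroidism names no grade and only says that therapy can go on. This is a general permission, which a specific prohibition can limit without contradiction.

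So two rows conflict clearly and one weakly.

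**Step 3: which events are caught.** By the Section 6.3.2.1 definition, a Grade 4 event need not carry immediate risk of death. The conflict then covers only events that were in fact life-threatening. Elsewhere the plan ties the word more closely to grade: Table 3 describes a Grade 4 infusion reaction as life-threatening, and Section 4.2.2 pairs severe with Grade 3. On that usage most Grade 4 events in the two rows would be caught. Either way, some are.

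**Step 4: whether any other text decides it.**

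- The lead-in to Section 4.2.2 says drug is withheld for severe or life-threatening events according to Table 2, which holds both rules.
- Section 4.4 refers dosing back to Section 4.2.2.
- Section 4.5 lists when treatment ends. It includes interruption beyond 12 weeks but has no item for a life-threatening event.
- The ECI guidance (Appendix C) was not available for review. Section 4.2.2 cites it for supportive care, not for dosing.
- The re-challenge sentence closing Section 4.2.2 stops a subject whose severe or life-threatening event recurs on re-challenge. It presupposes that re-dosing after such an event can happen, but does not say when.

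None of these sets a precedence.

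**Step 5: size.** The documents give no incidence. As an illustration only, let p be the chance per patient of a life-threatening event of these types, assumed to lie between 0.1% and 1%. With the 50 subjects of the Trial Summary, the expected number is 50p and the chance of at least one is 1 − (1 − p)^50.

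- p = 0.001: 0.05 patients expected; 1 − 0.999^50 = 4.9%.
- p = 0.005: 0.25 patients expected; 1 − 0.995^50 = 22.2%.
- p = 0.01: 0.5 patients expected; 1 − 0.99^50 = 39.5%.

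Nothing in the documents anchors this range, and the conclusion does not rest on it.

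**The case against.** The best answer is that the note is an overlay. The rows set defaults and the note adds stops that they omit. Its first half works this way: the Grade 3 colitis row allows restart without mentioning recurrence, and the note stops the patient if the event recurs. On this view the second half does the same for life-threatening events. If life-threatening has the Section 6.3.2.1 meaning, the Grade 4 entries keep a use for events without immediate risk of death. Following the note also adds no safety risk.

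This is a possible reading, and perhaps the intended one, but it does not remove the conflict. On recurrence the row is silent, so the note adds something. On Grade 4 hyperglycemia and hypophysitis the rows speak, and allow treatment again. Seven rows carry their own Grade 4 stop, so its absence here looks deliberate. If Section 4.2.2 uses severe for Grade 3 and life-threatening for Grade 4, letting the note prevail would largely empty those two Grade 4 entries. No text says which reading holds.

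The objection does stand against three stronger claims that a reader might infer:

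- *That three rows contradict the note equally.* Hypothyroidism has permissive wording and no grade, so it is only a weak case.
- *That every Grade 4 event in these rows is in conflict.* Grade 4 is spelled out as life-threatening only for infusion reactions, and the SAE definition is narrower.
- *That the re-challenge sentence is a further contrary rule.* It authorises no re-dosing. Its life-threatening part is merely idle if the note is applied strictly.

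**Conclusion.** The point holds in a narrow form. For a life-threatening event in the T1DM/hyperglycemia or hypophysitis row, the note and the row give opposite re-dosing instructions, and the text provided does not choose between them. This is an inconsistency in a safety rule, not missing detail, and it is worth correcting.

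The conclusion assumes that the event is drug-related, as the title of Table 2 implies, and that Appendix C contains no dosing rule that settles the matter. That few patients would be affected is a judgement, since no incidence is given. No sample size, error rate or analysis changes.

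**What to change.** Decide which rule is meant, and make note and rows agree.

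- **Default, unless the sponsor intends an endocrine exception.** Add to the T1DM/hyperglycemia and hypophysitis rows: *life-threatening event: permanently discontinue (see note)*. Tie the line to life-threatening events, not to Grade 4 as such, so that other Grade 4 events stay under the row. The downside is that a rare patient who stabilises on replacement loses further treatment.
- **If an exception is intended.** Attach it only to the second clause of the note: *any life-threatening event, except hypophysitis or T1DM/hyperglycemia that meets its row's restart criteria*. Do not let it reach the first clause, or recurrent severe or Grade 3 endocrine events would be exempted too. Keep the 12-week limits, both in the hypophysitis row and in the general text of Section 4.2.2.

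Under either option, leave the re-challenge sentence as a backstop. The cost is one line in each of two rows, or one clause in the note, with no change to visits, sample size or analysis.

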4.3 Concomitant Medications/Vaccinations (allowed & prohibited)

Medications or vaccinations specifically prohibited in the exclusion criteria are not allowed during the ongoing trial. If there is a clinical indication for one of these or other medications or vaccinations specifically prohibited during the trial, discontinuation from trial therapy or vaccination may be required. The final decision on any supportive therapy or vaccination rests with the investigator and/or the subject's primary physician. .

4.3.1 Acceptable Concomitant Medications

All treatments that the investigator considers necessary for a subject's welfare may be administered at the discretion of the investigator in keeping with the community standards of medical care. Concomitant medication will be recorded as standard of care in clinic database.

4.3.2 Prohibited Concomitant Medications

Subjects are prohibited from receiving the following therapies during the study.

- Any anti-cancer agents.
- Radiation therapy
 - Note: Radiation therapy to a symptomatic solitary lesion or to the brain will be allowed.
- Live vaccines within 30 days prior to the first dose of trial treatment and while participating in the trial. Examples of live vaccines include, but are not limited to, the following: measles, mumps, rubella, chicken pox, yellow fever, rabies, BCG, and typhoid (oral) vaccine. Seasonal influenza vaccines for injection are generally killed virus vaccines and are allowed; however intranasal influenza vaccines (e.g. Flu-Mist®) are live attenuated vaccines, and are not allowed.
- Glucocorticoids for any purpose other than to modulate symptoms of suspected immunologic etiology.

Subjects who, in the assessment by the investigator, require the use of any of the aforementioned treatments for clinical management should be removed from the trial. Subjects may receive other medications that the investigator deems to be medically necessary.

There are no prohibited therapies during the Post-Treatment Follow-up Phase.

4.4 Rescue Medications & Supportive Care

Subjects should receive appropriate supportive care measures as deemed necessary by the treating investigator. Suggested supportive care measures for the management of adverse events with potential immunologic etiology are outlined below and in greater detail in the ECI guidance document (Appendix C in PDOL). Where appropriate, these guidelines include the use of oral or intravenous treatment with corticosteroids as well as additional anti-inflammatory agents if symptoms do not improve with administration of corticosteroids. Note that several courses of steroid tapering may be necessary as symptoms may worsen when the steroid dose is decreased. For each disorder, attempts should be made to rule out other causes such as metastatic disease or bacterial or viral infection, which might require additional supportive care. The treatment guidelines are intended to be applied when the investigator determines the events to be related to pembrolizumab.

Note: if after the evaluation the event is determined not to be related, the investigator is instructed to follow the ECI reporting guidance but does not need to follow the treatment guidance (as outlined in the ECI guidance document). Refer to Section 4.2.2 for dose modification.

It may be necessary to perform conditional procedures such as bronchoscopy, endoscopy, or skin photography as part of evaluation of the event. Suggested conditional procedures, as appropriate, can be found in the ECI guidance document (Appendix C in PDOL).

- **Pneumonitis:**

- For **Grade 2 events**, treat with systemic corticosteroids. When symptoms improve to Grade 1 or less, steroid taper should be started and continued over no less than 4 weeks.
- For **Grade 3-4 events**, immediately treat with intravenous steroids. Administer additional anti-inflammatory measures, as needed.
- Add prophylactic antibiotics for opportunistic infections in the case of prolonged steroid administration.

- **Diarrhea/Colitis:**
Subjects should be carefully monitored for signs and symptoms of enterocolitis (such as diarrhea, abdominal pain, blood or mucus in stool, with or without fever) and of bowel perforation (such as peritoneal signs and ileus).
 - All subjects who experience diarrhea/colitis should be advised to drink liberal quantities of clear fluids. If sufficient oral fluid intake is not feasible, fluid and electrolytes should be substituted via IV infusion. For Grade 2 or higher diarrhea, consider GI consultation and endoscopy to confirm or rule out colitis.
 - For **Grade 2 diarrhea/colitis** that persists greater than 3 days, administer oral corticosteroids.
 - For **Grade 3 or 4 diarrhea/colitis** that persists > 1 week, treat with intravenous steroids followed by high dose oral steroids.
 - When symptoms improve to Grade 1 or less, steroid taper should be started and continued over no less than 4 weeks.

- **Type 1 diabetes mellitus (if new onset, including diabetic ketoacidosis [DKA]) or ≥ Grade 3 Hyperglycemia, if associated with ketosis (ketonuria) or metabolic acidosis (DKA)**
 - For **T1DM or Grade 3-4 Hyperglycemia**
 - Insulin replacement therapy is recommended for Type I diabetes mellitus and for Grade 3-4 hyperglycemia associated with metabolic acidosis or ketonuria.
 - Evaluate patients with serum glucose and a metabolic panel, urine ketones, glycosylated hemoglobin, and C-peptide.

- **Hypophysitis:**
 - For **Grade 2 events**, treat with corticosteroids. When symptoms improve to Grade 1 or less, steroid taper should be started and continued over no less than 4 weeks. Replacement of appropriate hormones may be required as the steroid dose is tapered.
 - For **Grade 3-4 events**, treat with an initial dose of IV corticosteroids followed by oral corticosteroids. When symptoms improve to Grade 1 or less, steroid taper should be started and continued over no less than 4 weeks. Replacement of appropriate hormones may be required as the steroid dose is tapered.

- **Hyperthyroidism or Hypothyroidism:**

Thyroid disorders can occur at any time during treatment. Monitor patients for changes in thyroid function (at the start of treatment, periodically during treatment, and as indicated based on clinical evaluation) and for clinical signs and symptoms of thyroid disorders.

- **Grade 2** hyperthyroidism events (and **Grade 3-4** hypothyroidism):

- In hyperthyroidism, non-selective beta-blockers (e.g. propranolol) are suggested as initial therapy.
 - In hypothyroidism, thyroid hormone replacement therapy, with levothyroxine or liothyroinine, is indicated per standard of care.

- **Grade 3-4** hyperthyroidism

- Treat with an initial dose of IV corticosteroid followed by oral corticosteroids. When symptoms improve to Grade 1 or less, steroid taper should be started and continued over no less than 4 weeks. Replacement of appropriate hormones may be required as the steroid dose is tapered.

- **Hepatic:**

- For **Grade 2** events, monitor liver function tests more frequently until returned to baseline values (consider weekly).
 - Treat with IV or oral corticosteroids
 - For **Grade 3-4** events, treat with intravenous corticosteroids for 24 to 48 hours.
 - When symptoms improve to Grade 1 or less, a steroid taper should be started and continued over no less than 4 weeks.

- **Renal Failure or Nephritis:**

- For **Grade 2** events, treat with corticosteroids.
 - For **Grade 3-4** events, treat with systemic corticosteroids.
 - When symptoms improve to Grade 1 or less, steroid taper should be started and continued over no less than 4 weeks.

- **Management of Infusion Reactions:** Signs and symptoms usually develop during or shortly after drug infusion and generally resolve completely within 24 hours of completion of infusion

Table 3 below shows treatment guidelines for subjects who experience an infusion reaction associated with administration of MK-3475.

Table 3 Infusion Reaction Treatment Guidelines

NCI CTCAE Grade	Treatment	Premedication at subsequent dosing
Grade 1		None

NCI CTCAE Grade	Treatment	Premedication at subsequent dosing
Mild reaction; infusion interruption not indicated; intervention not indicated	Increase monitoring of vital signs as medically indicated until the subject is deemed medically stable in the opinion of the investigator.	
Grade 2 Requires infusion interruption but responds promptly to symptomatic treatment (e.g., antihistamines, NSAIDS, narcotics, IV fluids); prophylactic medications indicated for <=24 hrs	
Stop Infusion and monitor symptoms. Additional appropriate medical therapy may include but is not limited to:
 
 IV fluids Antihistamines NSAIDS Acetaminophen Narcotics 
Increase monitoring of vital signs as medically indicated until the subject is deemed medically stable in the opinion of the investigator.
 
If symptoms resolve within one hour of stopping drug infusion, the infusion may be restarted at 50% of the original infusion rate (e.g. from 100 mL/hr to 50 mL/hr). Otherwise dosing will be held until symptoms resolve and the subject should be premedicated for the next scheduled dose.
 
Subjects who develop Grade 2 toxicity despite adequate premedication should be permanently discontinued from further trial treatment administration.
	Subject may be premedicated 1.5h (\pm 30 minutes) prior to infusion of MK-3475 with: Diphenhydramine 50 mg po (or equivalent dose of antihistamine). Acetaminophen 500-1000 mg po (or equivalent dose of antipyretic).
Grades 3 or 4 Grade 3: Prolonged (i.e., not rapidly responsive to symptomatic medication and/or brief interruption of infusion); recurrence of symptoms following initial improvement; hospitalization indicated for other clinical sequelae (e.g., renal impairment, pulmonary infiltrates) Grade 4: Life-threatening; pressor or ventilatory support indicated	
Stop Infusion. Additional appropriate medical therapy may include but is not limited to:
 
 IV fluids Antihistamines NSAIDS Acetaminophen Narcotics Oxygen Pressors Corticosteroids Epinephrine 
Increase monitoring of vital signs as medically indicated until the subject is deemed medically stable in the opinion of the investigator.
 
Hospitalization may be indicated.
 
Subject is permanently discontinued from further trial treatment administration.
	No subsequent dosing

Appropriate resuscitation equipment should be available in the room and a physician readily available during the period of drug administration.

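### Section 4.4 sets a later steroid trigger for Grade 3 or 4 diarrhea/colitis (more than 1 week) than for Grade 2 (more than 3 days), without giving a reason

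*Combined protocol and SAP*

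**What the plan says.** The Diarrhea/Colitis part of Section 4.4 (Rescue Medications & Supportive Care) has two adjacent bullets on when to start steroids:

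- Grade 2: an event "that persists greater than 3 days, administer oral corticosteroids".
- Grade 3 or 4: an event "that persists > 1 week, treat with intravenous steroids followed by high dose oral steroids".

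Section 4.2.2 (Dose Modification) relies on this text: "See Section 4.4 and Events of Clinical Interest Guidance Document for supportive care guidelines (Appendix C), including use of corticosteroids". Table 2 in that section covers study drug and sets no time for starting steroids. It holds MK-3475 for Grade 2-3 diarrhea/colitis and stops it permanently at Grade 4. After a Grade 2-3 hold, drug is discontinued on this condition: "Toxicity does not resolve within 12 weeks of last dose or inability to reduce corticosteroid to 10 mg or less of prednisone or equivalent". The steroid threshold is a daily dose, and the same 12 weeks apply to it.

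Other text sets the status of the two bullets. Section 4.4 opens with "Subjects should receive appropriate supportive care measures as deemed necessary by the treating investigator" and continues "Suggested supportive care measures for the management of adverse events with potential immunologic etiology are outlined below and in greater detail", pointing to Appendix C. The prohibited list in Section 4.3.2 reads "Glucocorticoids for any purpose other than to modulate symptoms of suspected immunologic etiology", so steroids for a suspected immune-related event are allowed at any time.

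**The concern.** One expects a steroid trigger to come no later as severity rises. Here the order is reversed. Taken literally, a drug-related event that has lasted more than 3 days but not more than a week has a steroid instruction if it is Grade 2 and none if it is Grade 3 or 4.

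Patient safety is the main issue. The same block asks staff to watch for bowel perforation, so the protocol itself treats enterocolitis as potentially dangerous. A secondary issue applies to Grade 3. Time spent waiting counts against the 12-week limit in Table 2, by which the event must have resolved and the steroid dose must have been reduced if the patient is to stay on study drug.

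**Working it through.** The plan states no figure to reproduce here. The check sets the two thresholds side by side, looks for a reason or an overriding instruction elsewhere, and sizes the difference.

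**1. The two thresholds (Section 4.4)**

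| Grade | Persistence before steroids | Steroid route |
|---|---|---|
| 2 | more than 3 days | oral |
| 3 or 4 | more than 1 week = more than 7 days | intravenous, then high-dose oral |

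Difference between the lower bounds: 7 - 3 = 4 days, with the longer wait on the higher grades.

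**2. The other Grade 3-4 steroid instructions in Section 4.4**

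| Toxicity | Grade 3-4 steroid instruction | Waiting period |
|---|---|---|
| Pneumonitis | intravenous, at once | none |
| Hypophysitis | intravenous, then oral | none |
| Hyperthyroidism | intravenous, then oral | none |
| Hepatic | intravenous for 24 to 48 hours | none |
| Renal failure or nephritis | systemic | none |
| Diarrhea/colitis | intravenous, then high-dose oral | more than 7 days |

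Diarrhea/colitis is the only toxicity in the section with a persistence condition before steroids, and that condition lengthens with severity.

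**3. Is there a reason or an override?**

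- Table 2 orders colitis by severity in the usual direction (hold at Grade 2-3, stop at Grade 4) but does not say when steroids start.
- Section 4.4 asks that other causes, including infection and metastatic disease, be ruled out. That request covers every disorder and every grade. The colitis work-up likewise starts at Grade 2: "For Grade 2 or higher diarrhea, consider GI consultation and endoscopy to confirm or rule out colitis". A work-up common to both grades cannot explain a shorter wait at Grade 2.
- Section 4.4 applies its treatment guidance to events that the investigator judges to be caused by pembrolizumab. The one-week condition therefore falls on events already attributed to the drug.

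The supplied text contains neither a reason nor an earlier trigger for Grade 3 or 4.

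**4. Size against the 12-week limit (Table 2; Grade 2-3 only)**

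The limit is 12 x 7 = 84 days from the last dose. Share used by the suggested wait:

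- Grade 3: 7/84 = 8.3%
- Grade 2: 3/84 = 3.6%
- Increment from the inversion: 4/84 = 4.8%

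The first two are minimum shares, because each wait is open-ended and fewer than 84 days remain when the event begins. As an illustration, assume onset when the next dose would have been due:

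| Assumed onset after last dose | Days left | Grade 3 wait | Grade 2 wait | Increment |
|---|---|---|---|---|
| 21 days (cycles 1-8) | 84 - 21 = 63 | 7/63 = 11.1% | 3/63 = 4.8% | 4/63 = 6.3% |
| 42 days (cycle 9 on) | 84 - 42 = 42 | 7/42 = 16.7% | 3/42 = 7.1% | 4/42 = 9.5% |

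The increment thus runs from 4.8% to 9.5% of the time available, depending on onset. Grade 4 is outside this calculation because drug is stopped permanently.

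**The case against.** The strongest case on the other side has five parts.

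- **Discretion.** The measures are suggestions, the investigator treats as judged necessary, and Section 4.3.2 permits earlier steroids. This stands, and it limits the point to a badly ordered default. It does not explain why the default has this order, and Section 4.2.2 sends readers to this text for steroid use.
- **Appendix C.** The fuller guidance was not supplied and could give another timing or a reason. This also stands. If it sets an earlier start, the protocol body conflicts with it. If it has the same order, the problem is in both places. If it gives a reason, Section 4.4 should carry it. Each outcome calls for the same check.
- **A cumulative reading.** Diarrhea at Grade 3 for more than 3 days has also been at least Grade 2 for that long. Oral steroids might then already be running, and the one-week condition would govern only escalation to intravenous treatment. This is possible but not the plainest reading, since each bullet is tied to its own grade. It would still delay intravenous steroids in the sickest patients.
- **Infection.** Deleting the wait might seem to invite high-dose steroids before infection is excluded. The work-up and the relatedness condition stand elsewhere in Section 4.4 and would still apply.
- **Size.** The link to the 12-week limit is modest, and nothing in the documents shows that 4 days would take any patient past it. This stands, so the recommendation rests on the order of the triggers and not on that link.

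**Conclusion.** The concern holds. The written steroid trigger for Grade 3 or 4 diarrhea/colitis is 4 days later than that for Grade 2. It is the only Grade 3-4 steroid instruction in Section 4.4 with a waiting period, and the supplied documents do not explain it. Only the steroid trigger is affected: the drug hold or stop, fluids, perforation monitoring, and consideration of GI consultation and endoscopy carry no duration condition.

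The conclusion rests on reading each bullet as applying to its own grade, and on the supplied text alone, since Appendix C could not be checked. The documents give no rate of Grade 3 or 4 colitis, so the number affected among the 50 planned patients is unknown. This is a safety-management wording defect with no bearing on the two-stage design or its error rates. It should be corrected because the correction costs almost nothing and the default, if followed, treats the sicker patient later.

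**What to change.** Remove the persistence condition from the Grade 3 or 4 bullet, so that an event of that grade judged related to study drug leads to intravenous and then high-dose oral steroids with no set wait. This matches the section's other Grade 3-4 steroid instructions. At minimum, set a wait no longer than the 3 days used for Grade 2. The clinical team should choose between the two and reconcile the bullet with Appendix C. If there is a clinical reason for the present order, it should be stated in Section 4.4.

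The cost is a wording amendment to one bullet and one cross-check. Sample size, data collection and analysis do not change.
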